	[name] Department of Infection, Immunity & Cardiovascular Disease University of Sheffield Medical School

[name]
Sheffield
[name]
UK
E: [contact]

[name]
Department of Infectious Disease Epidemiology
LSHTM
[name]
E: [contact]

[name]
Department of Infection, Immunity & Cardiovascular Disease
University of Sheffield
Medical School
[name]
Sheffield
[name]
UK
E: [contact]

Statistician: [name]
MRC Unit The Gambia at LSHTM
[name]
The Gambia
E: [contact]

Other Collaborators: institutions/ [name]
Department of Molecular Biology & Biotechnology,
The Florey Institute,
University of Sheffield,
Sheffield,
[name]
United Kingdom

E: [contact]

[name]
Genomics Laboratory Manager
MRC Unit The Gambia at LSHTM
[name]
The Gambia
E: [contact]

[name]
Paediatric Infectious Diseases and Immunity
London School of Hygiene and Tropical Medicine
[name]
E: [contact]

Clinical Laboratory/ies: Research Microbiology Laboratory
MRC Unit The Gambia at LSHTM
[name]
The Gambia

Genomics Facility
MRC Unit The Gambia at LSHTM
[name]
The Gambia

Local Ethics Committee Gambia Government/MRC Joint Ethics Committee,
c/o MRC Unit, The Gambia,
[name], The Gambia, West Africa

List of abbreviations

AE	Adverse Event
CRF	Case Report Form
CSD	MRCG Clinical Services Department
CSF	Cerebrospinal fluid
DMC	Data Monitoring Committee
GAS	Group A streptococcus
GCP	Good Clinical Practice
HIC	High-income countries
ICH	International Conference on Harmonization
IEC	Independent Ethics Committee
LMIC	Low- and middle-income countries
MDA	Mass drug administration
MRCG at LSHTM	Medical Research Council Unit The Gambia at London School of Hygiene & Tropical Medicine
MV0, MV1 etc.	Monthly visit 0, Monthly visit 1 etc.
PI	Principal Investigator
qPCR	Quantitative polymerase chain reaction
RHD	Rheumatic Heart Disease
WGS	Whole genome sequencing
WHO	World Health Organization

Protocol summary

Title:	Streptococcus pyogenes carriage acquisition, persistence and transmission dynamics within households in The Gambia: a longitudinal cohort study
Alias :	SpyCATS
Population:	Individuals within households in Sukuta
Number of participants:	45 households (approximately 450 individuals)
Number of Sites:	Household-based field study
Location of Sites (including satellite sites):	Field study in Sukuta Clinical Services Department MRCG Fajara Laboratories at MRCG Fajara
Study Duration:	18 months
Duration for Participants:	12 months
Objectives:	
Primary:
 
1. To determine the prevalence, incidence, duration and transmission dynamics of asymptomatic GAS carriage and clinical GAS infections within households.2. To establish risk factors for pharyngeal and skin clinical GAS infection, including detailed characterisation of the relationship with individual and household asymptomatic carriage, emm type and seasonality.3. To develop a mathematical model of household GAS transmission using clinical, behavioural and phylogenetic relatedness data to calibrate it, to allow for estimation of the relative contributions of between and within household transmission. 
Secondary:
 
1. To determine risk factors for asymptomatic GAS carriage.2. To describe the relative importance of asymptomatic GAS skin and throat carriage in this setting.3. To describe any seasonal variation in GAS carriage and clinical GAS infection throughout the year.4. To describe GAS emm type diversity in this setting.5. To investigate the extent of GAS tissue tropism of emm types identified.6. To determine the prevalence and incidence of groups C and G streptococcal carriage and clinical infection in this setting.7. To describe variations in bacterial density by site, season and clinical characteristics using quantitative PCR.

8. To describe anti-GAS seroprevalence and investigate serological responses to asymptomatic GAS carriage and clinical GAS infection.
9. To identify non-human reservoirs of GAS within households and the presence of airborne GAS indoors using settle plates.
10. To describe the antimicrobial sensitivity of GAS isolates identified.
11. To explore GAS-specific serological and mucosal immune activity in response to GAS colonization and disease, and to identify correlates of protection.

Endpoints:**Primary endpoints:**

- Asymptomatic GAS throat and skin carriage and clinical GAS infection prevalence at each monthly visit
- Asymptomatic GAS throat and skin carriage and clinical GAS infection incidence per person year
- Duration of asymptomatic GAS throat and skin carriage to the nearest week
- Phylogenetic relatedness of GAS isolates by whole genome sequencing
- Clinical examination findings and features of clinical GAS infection

Secondary endpoints:

- Presence of risk factors for GAS carriage or disease at individual and household levels
- Seasonal variation in GAS carriage and infection prevalence
- GAS *emm* type
- Groups C and G streptococcal prevalence and incidence
- Quantification of bacterial presence by qPCR
- GAS serological responses (including seroprevalence and fold-change in antibody titres in response to asymptomatic carriage and clinical infection).
- GAS presence on household swabbing and settle plates
- GAS antimicrobial sensitivity

Description of Study Design: A prospective cohort study within households in Sukuta, The Gambia, will be conducted. A total of 45 households will be recruited, including every household member as individual participants (resulting in approximately 450 participants).

Participants will be enrolled for 12 months, covering one full rainy season, undergoing an enrolment visit (MV0), then monthly visits (MV1, MV2, MV3, etc. until MV12). At each visit an oropharyngeal and normal skin swab, a saliva sample and

a dried blood spot (DBS) will be taken, data collected on socio-demographics, social-mixing/behavioural factors and clinical examination findings. Swabs will also be taken from any pyoderma lesions, environmental swabs from common touch points and settle plates used inside households. In addition, a blood for a serum sample will be taken at the enrolment and final visits.

A subgroup of 16 random households, will undergo more frequent (weekly) throat and skin swabbing for a period of 6 weeks, during the second 6 months of the study.

Weekly swabs will also be taken from participants who become GAS (or GCS/GGS) carrier positive within the first 6 months, until they have had 2 negative swabs.

Participants reporting symptoms suggestive of possible clinical GAS infection such as pharyngitis or pyoderma (but also including invasive infections), will be visited for an unscheduled visit where a clinical and health-seeking history will be recorded, a swab, a saliva sample and a DBS taken, and treatment (or further management) will be delivered according to WHO guidelines.

Swabs from participants will be cultured for the presence of GAS (and GCS/GGS) and isolates will undergo whole genome sequencing (WGS) in order to assess phylogenetic relatedness of strains identified. These data, combined with temporal incidence of strain acquisition, clinical data and household situation will be used to build a mathematical model of GAS transmission to identify key routes of transmission within and between households in The Gambia.

1 Background information and rationale

1.1 Background information

Group A Streptococcus (*Streptococcus pyogenes*, GAS) is a beta-haemolytic Gram positive bacterium that is a major cause of infectious disease burden globally, responsible for over half a million annual deaths (1-4). It causes a wide spectrum of disease from superficial skin and pharynx infections through to invasive disease, in addition to the immunological sequelae of acute rheumatic fever, rheumatic heart disease (RHD) and acute post-streptococcal glomerulonephritis (3, 5). Each year an estimated 1.8 million invasive GAS, 111 million pyoderma and 616 million pharyngitis cases are thought to occur globally (2). The majority of clinical GAS infections are thought to occur in low-income countries, though the data from such countries is the most lacking (1, 2, 6, 7).

Rheumatic heart disease, the most serious immunological consequence of GAS infection, causes over 300,000 deaths each year, predominantly in low- and middle-income countries (LMIC) (3). RHD surveillance data from Africa are lacking, prevalence estimates in sub-Saharan Africa (sSA) range between 7.4 and 51.6 per 1000 children (8). Ethiopian children with RHD were shown to have a 12.5% annual mortality rate (9).

Despite the significant burden of disease caused by GAS and its immunological sequelae globally and particularly in LMIC such as The Gambia, data are limited on interventions to reduce GAS carriage, transmission and associated disease in LMIC (10, 11). Furthermore, the understanding of the natural history of GAS carriage, transmission and infection is limited. An understanding of carriage duration, sociodemographic and behavioral factors affecting carriage and transmission, seasonal variation, the relationship between carriage and disease, and transmission patterns within households are all crucial in order to design and implement interventions targeting GAS in LMIC. The limited understanding that we have on these aspects of GAS are mostly from high-income countries (HIC) (12-14). In LMIC, higher prevalence and incidence of GAS carriage may underlie the higher burden of GAS-related clinical infections and immune sequelae seen (1-3).

The epidemiology of superficial GAS infections in The Gambia is poorly understood, therefore in 2018 we conducted a cross-sectional study in Sukuta in 1441 children under 5 to determine the prevalence of common skin infections including GAS pyoderma and scabies, which is important in pyoderma prevalence due to the common presence of bacterial co-infection of scabies lesions. We showed a high prevalence bacterial pyoderma (17.4%), and scabies infestation (15.9%), and specifically of GAS culture-positive pyoderma (8.8%). We also found a significant increase in pyoderma during the rainy season (before the start of the rains vs. after: 8.9% vs. 23.1%, aPR 2.42, CI 1.39-4.23).

Whole-genome sequencing (WGS) has transformed our ability to understand GAS epidemiology, giving significant resolution to determine linkage between strains. WGS has been critical in GAS outbreak investigations in HIC (15-18), but has not been used in African settings. Combining phylogenetic relatedness data from WGS, clinical and behavioural data with mathematical models can provide new insights into transmission dynamics and potential intervention strategies, and has not been attempted for GAS in any LMIC setting before.

References of literature and data are listed in Section 14.

1.2 Rationale

Despite the significant burden of disease caused by GAS in LMIC, prevention and treatment of GAS disease is lacking. In HIC, superficial GAS infections such as pharyngitis and pyoderma (impetigo) are typically diagnosed early and often treated with antibiotics, within well-developed primary healthcare systems. In low-resource settings, where living conditions and environment often put people at higher risk of GAS infections, and primary healthcare is more limited, a different model of care is required to tackle the burden of GAS disease. While effective vaccines against GAS have not yet been developed, mass drug administration (MDA) of scabicides such as ivermectin, in areas where scabies is a major driver of GAS, have been shown to be an effective method at reducing GAS infections for a prolonged period of time following a single administration of MDA, and could be increasingly used in low-resource settings (19-21).

Whether MDA directly targeting GAS, for example with Azithromycin, might be an effective strategy is unknown at this time. Theoretically, MDA might be effective in reducing GAS infections in a population due to treatment of active GAS infections reducing the pool of contagious individuals, and thus reducing the risk of transmission of GAS from an infected person to a non-infected person. However, it might also be effective at reducing the rates of asymptomatic carriage of GAS in the population, and thus reducing spread of GAS from asymptomatic carriers to non-infected people and non-carriers. WGS of GAS isolated from The Gambia showed a much higher *emm* type diversity than in HIC, suggesting that infection acquisition may be related to widespread carriage and transmission rather than highly clonal large single-strain outbreaks as seen in HIC (17, 18, 22). The role of asymptomatic pharyngeal carriage and non-pharyngeal reservoirs of GAS such as skin and environmental sources are not well understood.

To understand if MDA might be effective at reducing GAS outside of the context of scabies control, and to better understand how, when and where MDA should be used in future in regions such as The Gambia, it is essential to understand the natural history of GAS carriage, persistence, transmission dynamics and clinical infection. We have shown a high level of GAS skin infections in The Gambia in a cross-sectional study, but in order to understand the temporal relationship between carriage and disease, how GAS is spread from person to person, via skin or pharynx, acquired inside or outside households, and other risk factors for carriage and disease, a longitudinal study is essential. Very few longitudinal studies of GAS exist (12, 23), and high quality data from high-prevalence countries in sub-Saharan Africa combining classical epidemiology with detailed social-mixing behaviour and next generation WGS techniques to model disease transmission will be highly informative in growing our understanding of GAS epidemiology.

2 Study objectives

Primary:

1. To determine the prevalence, incidence, duration and transmission dynamics of asymptomatic GAS carriage and clinical GAS infections within households.
2. To establish risk factors for pharyngeal and skin clinical GAS infection, including detailed characterisation of the relationship with individual and household asymptomatic carriage, *emm* type and seasonality.
3. To develop a mathematical model of household GAS transmission using clinical, behavioural and phylogenetic relatedness data to calibrate it, to allow for estimation of the relative contributions of between and within household transmission.

Secondary:

1. To determine risk factors for asymptomatic GAS carriage.
2. To describe the relative importance of asymptomatic GAS skin and throat carriage in this setting.
3. To describe any seasonal variation in GAS carriage and clinical GAS infection throughout the year.
4. To describe GAS *emm* type diversity in this setting.
5. To investigate the extent of GAS tissue tropism of *emm* types identified.
6. To determine the prevalence and incidence of groups C and G streptococcal carriage and clinical infection in this setting.
7. To describe variations in bacterial density by site, season and clinical characteristics using quantitative PCR.
8. To describe anti-GAS seroprevalence and investigate serological responses to asymptomatic GAS carriage and clinical GAS infection.
9. To identify non-human reservoirs of GAS within households and the presence of airborne GAS indoors using settle plates.
10. To describe the antimicrobial sensitivity of GAS isolates identified.
11. To explore GAS-specific serological and mucosal immune activity in response to GAS colonization and disease, and to identify correlates of protection.

2.1 Study endpoints**Primary endpoints:**

- Asymptomatic GAS throat and skin carriage and clinical GAS infection prevalence at each monthly visit
- Asymptomatic GAS throat and skin carriage and clinical GAS infection incidence per person year
- Duration of asymptomatic GAS throat and skin carriage to the nearest week
- Phylogenetic relatedness of GAS isolates by whole genome sequencing
- Clinical examination findings and features of clinical GAS infection

Secondary endpoints:

- Presence of risk factors for GAS carriage or disease at individual and household levels
- Seasonal variation in GAS carriage and infection prevalence
- GAS *emm* type
- Groups C and G streptococcal prevalence and incidence
- Quantification of bacterial presence by qPCR
- GAS serological responses (including seroprevalence and fold-change in antibody titres in response to asymptomatic carriage and clinical infection).
- GAS presence on household swabbing and settle plates
- GAS antimicrobial sensitivity

3 Study design

3.1 Type of study and design

The proposed study is a prospective, longitudinal (open) cohort study within households in Sukuta, The Gambia. Households will be recruited, and all household members present at the time of the visit will be asked to participate. Households will be followed for 12 months, with monthly visits, and more frequently for some subgroups of participants.

A total of 45 households will be recruited, including every available consenting household member as individual participants (resulting in approximately 450 participants with the average household size being around 10 in Sukuta).

Households will be enrolled for 12 months, with enrolment aiming to commence before the rainy season, to ensure that the enrolment period will span one full rainy season, with dry periods either side. Every household will undergo an enrolment visit (MV0), then monthly visits (MV1, MV2, MV3 etc., up to MV12) or less frequently if practical constraints arise. At each visit, the household size will be determined by the number of individuals who slept in the household the previous night, and those household members present will be asked to participate. Household members not available to be seen will be still allocated a household ID number, in order to capture relevant information regarding their social mixing with other household members, and if they are present at later visits, they will be asked to enrol. Participants who's baseline (enrolment) visit occurs after MV0 will be asked why they were not available previously. Reasons for missed visits and late enrolment will be captured.

At each visit an oropharyngeal (OPS), normal skin swab (NSS), oral fluid (OF) and dried blood spot (DBS) will be taken from all individuals present, data collected on socio-demographics, behavioural factors and clinical examination findings. In addition, a blood sample for serum (BS) may be taken at the beginning and end of the study for detailed functional immune responses. This may be done by arranging a clinic visit if more appropriate. Swabs will also be taken from any pyoderma lesions, from common touch points in the household such as door handles, and settle plates (SP) used inside households. Throughout the study, if an enrolled participant reports symptoms consistent with GAS infection, they will have an unscheduled visit including a physical examination an appropriate swab (oropharyngeal or pyoderma), OF and DBS. Swabs will be taken the same day to the research microbiology laboratory and plated for culture. The culture will identify the presence of GAS (and Groups C and G Streptococcus) from the swabs, antibiotic resistance will be determined and any GAS (and GCS and GGS) isolates will be stored for later use. Skin and pyoderma swabs will also be cultured for *Staphylococcus aureus* and isolates stored for later use. Additional clinical samples will be taken at various time-points including serum blood samples, dried blood spot and salivary samples to contribute to exploratory objectives.

Swabs from participants will be cultured for the presence of GAS and isolates will undergo whole genome sequencing (WGS) in order to assess phylogenetic relatedness of strains identified. These data, combined with temporal incidence of strain acquisition, clinical data and household situation will be used to build a mathematical model of GAS transmission to identify key routes of transmission within and between households.

[figure not shown]

Figure 1. Visit and sampling schedule schematic

3.2 Sub-studies

3.2.1 Intensified incident GAS surveillance cohort

A subgroup of 16 randomly selected households will form a cohort to undergo intensified swabbing. This cohort will be used to assess incidence and duration of GAS carriage and disease with greater resolution than the main cohort. All household members present will undergo more frequent swabbing (OPS and NSS), with a view to being visited every week for 6 weeks. At these visits, more detailed social-mixing behaviour data will be collected. This more intensive temporal epidemiology with the social-mixing behavioural data collected will be combined with WGS data to inform the household transmission model.

3.2.2 Estimating duration of GAS carriage

A further subgroup will also be identified to allow for greater resolution in the estimation of the duration of GAS (and GCS/GGS) carriage. Following MV0, any participant who becomes GAS (or GCS/GGS) carrier positive (i.e. was negative at baseline or the previous visit, and then becomes positive at a monthly visit) will have weekly swabs taken from the same site that was positive, until 2 GAS negative swabs have been taken in a row.

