5.3.6 Weekly visits for asymptomatic GAS (or GCS/GGS) carriers

All participants not already in the intensified incident GAS cohort, who's OPS or NSS grow GAS (or GCS/GGS) on culture at a monthly visit following a previous negative swab, will be classified as "new carriers" who will then be swabbed weekly until such time as 2 negative swabs in a row have been obtained from the same site that was positive i.e. a participant who's OPS was positive at MV1 will have weekly OPS until negative twice in a row, whereas a participant with a positive NSS will have weekly NSS.

At these weekly visits, only the household member who is a "new carrier" will be seen and swabbed, not the other household members. The study team will ask a brief medical history, perform a physical examination, and take the swab from the previous positive site. If the participant has developed any clinician symptoms potentially in connection with their positive swab, then they will be treated as a GAS infection case as described in section 5.3.4.

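### The stop rule for weekly swabbing in section 3.2.2 names only GAS, so a carrier of group C or G alone can leave follow-up after two visits while still carrying

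*Protocol*

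**What the plan says.** Section 3.2.2 sets up a subgroup to give "greater resolution in the estimation of the duration of GAS (and GCS/GGS) carriage". Entry is open to "any participant who becomes GAS (or GCS/GGS) carrier positive", meaning someone negative before and positive at a monthly visit. Such a participant "will have weekly swabs taken from the same site that was positive, until 2 GAS negative swabs have been taken in a row".

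Section 5.3.6 gives the visit procedure for the same participants. Its entry condition is a throat or skin swab that will "grow GAS (or GCS/GGS) on culture at a monthly visit following a previous negative swab". Its stop condition is that "2 negative swabs in a row have been obtained from the same site that was positive", with no organism named.

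The protocol summary describes the same follow-up as lasting "until they have had 2 negative swabs". It names no organism and does not require the two swabs to be consecutive.

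Three other parts of the protocol bear on this:
- Section 5.6.2 has beta-haemolytic, catalase-negative colonies typed for Lancefield groups A, C and G.
- Section 5.3.3 keeps throat and skin swabs going at each monthly visit for every participant.
- Section 2.1 lists duration as an endpoint for GAS only. For groups C and G it lists prevalence and incidence.

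**The concern.** Within section 3.2.2 the aim and the entry rule cover both kinds of organism, but the exit rule covers one. A participant who qualified on group C or G and has no GAS at that site is GAS negative from the first weekly visit. Two such visits end follow-up, and the result for the qualifying organism plays no part in the decision.

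This is a sampling rule, so its effect cannot be repaired at analysis: weekly swabs that were not taken cannot be recovered. At stake is the weekly resolution for GCS/GGS carriage that section 3.2.2 sets out to obtain. Because the other two statements of the rule are worded differently, field staff could also stop follow-up at different points depending on which section they work from.

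**Working it through.** The protocol gives no figure for GCS/GGS carriage duration, so there is nothing to reproduce. The check compares the wording first and then illustrates the size.

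**1. The three stop rules side by side**

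| Place | Organism named | Consecutive? | Group C or G carrier without GAS, still growing C or G at weeks 1 and 2 |
|---|---|---|---|
| Summary | none | not stated | naturally read as not negative: continue |
| 3.2.2 | GAS | yes | both swabs are GAS negative: stop |
| 5.3.6 | none | yes | naturally read as not negative: continue |

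The same participant stops under one section and continues under the other two. No section says negative for the group that qualified the participant, and nothing in the protocol says which section prevails. The schedules show the same drift: the duration column is headed for new carriers in Table 1 (section 5.4) but for new GAS carriers in the appendix schedule.

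**2. What remains if 3.2.2 is followed**

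The two weekly swabs and all later monthly swabs are still typed for groups A, C and G. A carrier whose organism has gone by week 2 keeps a weekly bracket for the end of carriage. A carrier still positive at week 2 has only the monthly swabs after that.

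Section 4.3.1 and Table 1 allow each monthly visit to move by 14 days either way. Taking a 30-day month:
- Nominal gap between monthly swabs: 30 days.
- Largest gap within the windows: 30 + 14 + 14 = 58 days.
- Gap under weekly swabbing: nominally 7 days.

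The appendix schedule gives a monthly window of 7 days either way, which would make the largest gap 30 + 7 + 7 = 44 days. On either figure the bracket is several times wider than a week.

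**3. How many carriers would be affected**

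Assume clearance at a constant rate with mean duration m weeks, counted from the qualifying swab, with weekly visits at weeks 1 and 2. Then

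P(still carrying at week 2) = exp(−2/m).

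| Assumed mean m (weeks) | exp(−2/m) | Still carrying at week 2 |
|---|---|---|
| 1 | exp(−2) | 14% |
| 2 | exp(−1) | 37% |
| 4 | exp(−0.5) | 61% |
| 12 | exp(−0.167) | 85% |

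These shares apply only to GCS/GGS carriers with no GAS at the sampled site. Someone who also carries GAS there would not meet the 3.2.2 rule at the first two visits.

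**The case against.** The best defence is that section 3.2.2 is an overview and section 5.3.6 is the procedure. Section 5.3.6 is headed for GAS and GCS/GGS carriers, and in that setting a swab growing group G from a group G carrier would not ordinarily be called negative. The summary points the same way. On this view the word GAS in the 3.2.2 stop rule is a slip, and follow-up would go on as intended. This has real force, and it is why the point is a conflict between sections and not a design bound to fail. It does not remove the conflict. Section 3.2.2 is the only one of the three that names an organism, so a reader could take it as the definition of negative.

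Three stronger readings are tempting, and the protocol does not support them.

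- **A reader might infer that GCS/GGS duration cannot be derived at all.** Monthly swabs continue and are typed for all three groups, so duration would still be bracketed, only more coarsely. The 16 intensified households (sections 3.2.1 and 5.3.5) also have weekly swabs for up to 6 weeks whatever this rule says, although that fixed period is not follow-up to clearance.
- **A reader might infer that the unqualified wording of 5.3.6 lengthens a GAS episode when group C or G appears after GAS has cleared.** It could lengthen the period of swabbing. It does not set the end of an episode, and typed cultures would show when GAS was last found.
- **A reader might infer that different sites will apply different rules.** This is one household field study in Sukuta, and no multi-site divergence is described.

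It is also fair to say that no listed endpoint is lost. Secondary objective 6 asks only for GCS/GGS prevalence and incidence. GCS/GGS duration is an aim of section 3.2.2 and nothing more, and for GAS carriers the 3.2.2 rule works as written.

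**Conclusion.** The point holds as an inconsistency in a sampling rule. Section 3.2.2, followed literally, stops weekly swabbing of a carrier of group C or G alone after two visits regardless of whether that organism has cleared. Section 5.3.6 and the summary conflict with it, and none of the three ties the stop to the qualifying group.

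The loss is limited to weekly resolution for GCS/GGS carriage beyond week 2. It arises only where 3.2.2 is followed in preference to 5.3.6. The primary GAS duration endpoint does not depend on it.

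The size is uncertain. The range of 14% to 85% still carrying at week 2 comes from assumed mean durations of 1 to 12 weeks and constant-rate clearance, and the protocol gives no basis for choosing within it. The point still merits a change to the text, because the lost swabs could not be replaced later and the correction is small.

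**What to change.** State one rule in the summary, section 3.2.2 and section 5.3.6: weekly swabbing continues until two consecutive swabs from the same site are negative for the Lancefield group (A, C or G) that qualified the participant. Give the duration column of the appendix schedule the same heading as Table 1, so that it does not suggest a GAS-only cohort.

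The cost is one sentence in each of the three places, and a few more weekly swabs for persistent GCS/GGS carriers than section 3.2.2 requires as written. No new assay is needed, because the laboratory procedure already types for groups A, C and G.
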